5.3.3 Removal of Subjects

Subjects may withdraw or be withdrawn from the study for the following reasons:

- 1. At their own request or at the request of their legally acceptable representative.
- 2. If, in the investigator's opinion, continuation in the study would be detrimental to the subject's well-being.
- 3. At the specific request of the sponsor*
- * Subjects will only be removed at the request of the sponsor if a safety concern is identified that may potentially cause harm to a subject or if the risk of the specified treatment outweighs the benefit.
- 4. Post-consent decision due to inclusion error (determination of ineligibility based on safety or eligibility criteria).
- 5. Physician's judgment following an AE after treatment.
- 6. Termination of the study by a regulatory authority.

In all cases, the reason for withdrawal must be recorded in the eCRF and in the subject's records.

5.3.4 Subject Replacement

Subjects who are randomized and withdrawn from the study will not be replaced.

5.3.5 Follow-up of Subjects Withdrawn from Study

If possible, blood samples will be obtained to complete all pertinent tests at the time of subject withdrawal. In all cases, the reason for withdrawal must be recorded in the eCRF and in the subject's records. No subject can be re-enrolled into the study after having been withdrawn from the study.

Subjects who receive any amount of IP and discontinue early from the study should have all Month 12/Early Discontinuation visit procedures performed at the time of withdrawal (preferably within 1 week of withdrawal).

All efforts should be made to collect the vital status of the subject (including data on liver transplantation, subject survival, and cause of death) at Months 3, 6, and 12.

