- 12v5. Subjects with nephropathy with renal failure with serum creatinine >2 mg/dL or systemic hypertension.
- 13v5. This criterion has been removed from protocol Version 5.
- 14. Subjects with severe psychiatric disorders.

- 15. Subjects with a known infection with human immunodeficiency virus (HIV) or have clinical signs and symptoms consistent with current HIV infection.
- 16. Females who are pregnant, breastfeeding, or if of childbearing potential, unwilling to practice effective methods of contraception (oral, injectable, or implanted hormonal methods of contraception, placement of an intrauterine device or intrauterine system, condom, or occlusive cap with spermicidal foam/gel/cream/suppository, male sterilization, or true abstinence*) throughout the study.
 - * True abstinence: When this is in line with the preferred and usual lifestyle of the subject (periodic abstinence [eg, calendar, ovulation, symptothermal, post-ovulation methods], declaration of abstinence for the duration of the clinical study, and withdrawal are not acceptable methods of contraception).
- 17. Subjects with previous liver transplantation.
- 18. Subjects with known or suspected hypersensitivity to albumin.
- 19. Subjects participating in another clinical study within 3 months prior to screening.
- 20v4. Subjects with active drug addiction (exceptions: active alcoholism or marijuana).
- 21. In the opinion of the investigator, the subject may have compliance problems with the protocol and the procedures of the protocol.
- 22. Subjects with ongoing or recent variceal bleeding (subjects can be included 2 weeks after hemorrhagic episode).
- 23. Subjects with septic shock at screening.
- 24. Subjects with ongoing SBP infection (subjects can be included upon resolution).
- 25. Subjects with current infection of COVID19, those who are less than 14 days post recovery, or those who have clinical signs and symptoms consistent with COVID19 infection.

Investigational Product, Dose and Mode of Administration

Albutein 20% is the investigational product (IP).

Following randomization, subjects will receive the first Albutein 20% infusion at the dose of 1.5 g/kg body weight (maximum 100 grams per subject). Thereafter, subjects will receive Albutein 20% infusions at the dose of 1.5 g/kg body weight (maximum 100 grams per subject) every 10 ± 2 days for the rest of the study (up to a maximum of 12 months). Subjects in this treatment group will also receive SMT.

Duration of Treatment:

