4.4 Study Treatments

4.4.1 Treatments to Be Administered

4.4.1.1 Standard Medical Treatment + Albutein 20%

Albutein 20% is the IP in this study and is purified from human plasma. The solution is normally clear to slightly opalescent. Do not use the IP if the solution is cloudy or has precipitated. The product must be warmed to room temperature before use.

Do not dilute with water for injection. Once the container is open, the content must be administered immediately. Unused content must be discarded.

For additional information, see the IB.

Subjects allocated to this treatment group will receive SMT + Albutein 20%.

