7.2.1.2.4 MONTH 12 VISIT/ EARLY DISCONTINUATION VISIT

All assessments and activities at the Month 12 (Day $361 \pm 2 \text{ days}$)/Early Discontinuation Visit will be performed prior to treatment. In the SMT + Albutein 20% treatment group, vital signs and serum albumin concentration will also be recorded after treatment. Study assessments and activities will include:

- Record vital signs (systolic and diastolic BP, HR, RR, T) (measured immediately prior to and immediately after the end of the Albutein 20% infusion in the SMT + Albutein 20% treatment group)
- Ascites assessment according to the ICA criteria (Appendix 2)
- Hepatic encephalopathy evaluation (Appendix 4)
- Hemodynamics assessment (MAP)
- Peripheral capillary oxygen saturation (SpO₂) assessment
- Assessment of TIPS insertion
- Record weight
- Blood sample collection for (see Table 7-1):
 - Clinical laboratory assessments (eg, hematology, chemistry, coagulation)
 - Serum albumin concentration (measured immediately prior to and immediately after the end of the Albutein 20% administration in the SMT + Albutein 20% treatment group [Month 12 Visit only])
 - Systemic inflammatory assessment
 - Albumin functional capacity assessment in serum (albumin binding capacity)

- Blood biomarker retains (optional, all clinical blood samples will need to be drawn first)
- Record ACLF grade (see Table 2-1)
- Illness severity scores evaluation: CLIF-C OF score, CLIF-C AD score, CLIF-C ACLF score, MELD score, and Child Pugh score (Appendix 3).
- Physical examination
- Record concomitant medications
- Quality of life assessment (EQ-5D-5L health questionnaire [Appendix 5])
- Record AEs
- Record data on liver transplantation, subject survival, and cause of death
- Albutein 20% infusion (SMT + Albutein 20% treatment group [Month 12 Visit only])

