5.2.5 Month 12 / Early Discontinuation

All subjects will have assessments at Month 12 (Day 361 ± 2 days)/Early Discontinuation. Subjects in the SMT + Albutein 20% treatment group will receive an Albutein infusion at Month 12. All assessments and activities will be performed prior to treatment for SMT + Albutein 20% treatment group. In the SMT + Albutein 20% treatment group, vital signs and serum albumin concentration will also be recorded after Albutein infusion.

Subjects who discontinue from the study early will complete the assessments that are planned for the Month 12 visit.

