6.1.5 Visit Windows

For safety analyses (laboratory and vital signs data) and efficacy analyses, by-visit summaries and analyses will analyze assessments by visit as designated on the CRF; visit remapping based on study day to an analysis visit window won't be applied. Unscheduled visits will be excluded from by-visit summaries and analyses. The Early Discontinuation

GRIFOLS	Bioscience Industrial Group	Number	IG1601	Version	2.0	Status	Effective	Effective Date	09-Sep-2024	Page	20 of 52
		IG1601	Statistical Analysis Plan								

visit will be summarized as a separate visit, without adjusting for the timing of assessments for subjects that discontinue early.

For the analyses of exploratory endpoints, the early discontinuation visit will be mapped to an assessment visit. The mapping will be based on the timing of a subject's assessment visit, relative to their Study Day 1. A detailed list of the parameters and the mapping rules to be applied is provided in [Appendix 4](#).

For cases where multiple assessments are recorded for a parameter within a single visit window, the following rules will be applied for each parameter:

- If 2 or more assessments are mapped to the same visit window, then the non-missing assessment closest to the scheduled visit target day will be used in the analysis.
- If 2 assessments are equidistant from the visit target day, the later non-missing observation will be used in the analysis.

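### Protocol 5.3.5 ties the Early Discontinuation visit to having received Albutein, while the visit description, the schedule and the SAP expect it of every early leaver

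*Protocol*

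**What the plan says.** Protocol 5.3.5, on subjects withdrawn from the study, states: "Subjects who receive any amount of IP and discontinue early from the study should have all Month 12/Early Discontinuation visit procedures performed", ideally within a week of withdrawal. Section 4.4.1.1 fixes the meaning of IP: "Albutein 20% is the IP in this study and is purified from human plasma". The synopsis defines it the same way.

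Three other requirements in 5.3.5 carry no IP condition:
- Blood sampling: "If possible, blood samples will be obtained to complete all pertinent tests at the time of subject withdrawal".
- The reason for withdrawal is recorded.
- Vital status, including transplantation and cause of death, is sought at Months 3, 6 and 12.

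Elsewhere the visit has no IP condition. Protocol 7.2.1.2.4 describes one Month 12/Early Discontinuation (ED) visit and singles out the active arm only for additions: "In the SMT + Albutein 20% treatment group, vital signs and serum albumin concentration will also be recorded after treatment". Protocol Appendix 1 has a single column for the visit. SAP 5.2.5 is explicit: "All subjects will have assessments at Month 12 (Day 361 ± 2 days)/Early Discontinuation", and "Subjects who discontinue from the study early will complete the assessments that are planned for the Month 12 visit".

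The ED data are used in the analysis. For exploratory endpoints, SAP 6.1.5 says "the early discontinuation visit will be mapped to an assessment visit".

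**The concern.** A visit rule that depends on having received IP is, in this trial, a rule that depends on treatment arm. The trial is open-label, so a site always knows whether the condition applies.

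If 5.3.5 were followed literally, an infused Albutein subject who withdrew would have the full set of closing assessments: ascites, encephalopathy, arterial pressure, oxygen saturation, laboratory tests, ACLF grade, severity scores, quality of life and adverse events. An SMT subject who withdrew would have blood drawn if feasible and vital status follow-up. The exploratory analyses could then contain values at dropout for one arm and lack them for the other. SAP 6.1.1 does not impute missing values explicitly, so nothing later in the plan restores the balance.

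Adverse event recording is also involved. Protocol 8.2.1 and 8.3.8 end it at the End of Study or ED visit. An SMT leaver without an ED visit has no clear closing date.

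**Working it through.** No figure in the plan depends on this point. The check is a comparison of wording, followed by a bound on the number of subjects.

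**1. Who is asked for the ED visit**

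| Place | Who has the visit |
|---|---|
| Protocol 5.3.5 | Early leavers who received any IP |
| Protocol 7.2.1.2.4 | No arm or IP limit; only the post-treatment measurements and the infusion are specific to Albutein |
| Protocol Appendix 1 | One column, no IP limit; a few items are footnoted as Month 12 only |
| SAP 5.2.5 | All subjects; early leavers complete the Month 12 assessments |

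Section 5.3.5 is the outlier. It is also the section devoted to withdrawn subjects, and it gives the timing relative to withdrawal. The SAP cannot settle what sites do: it is an analysis document effective 09-Sep-2024, while protocol version 6.0 is effective 24-Sep-2020.

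**2. What an SMT leaver would lack under a literal reading**

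The score formulas in Protocol Appendix 3 show which inputs come from blood alone:
- MELD uses creatinine, bilirubin and INR. CLIF-C AD uses age, creatinine, INR, white cells and sodium. The blood draw in 5.3.5 could supply these, if it is obtained.
- Child-Pugh also needs encephalopathy and ascites. CLIF-C OF also needs encephalopathy, arterial pressure and respiratory status, and CLIF-C ACLF is built on CLIF-C OF. Blood alone does not supply these.
- ACLF grade depends on organ failures and encephalopathy, so it has the same gap.

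**3. Which analyses use the visit**

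SAP Appendix 4 maps the ED visit to windows for ACLF, CLIF-C OF, CLIF-C ACLF, CLIF-C AD, MELD, Child-Pugh, serum albumin and albumin binding capacity. SAP 9.3.1 counts ACLF as at least one occurrence, so an added assessment in one arm can only add detected cases there. The total scores go into repeated-measures models (SAP 9.3.2 to 9.3.5).

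The primary and the five time-to-event secondary endpoints need only death and transplant dates. These are sought at Months 3, 6 and 12 for all early leavers (Protocol 5.3.5 and 7.2.1.4; SAP 5.2.7). SAP 6.1.4 also accepts the withdrawal date as a last-contact date, so censoring does not rest on the ED visit.

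**4. How many subjects could be exposed**

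Inputs: about 205 SMT subjects (Protocol 4.2) and 20% assumed dropout (Protocol 9.2).

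Exposed SMT subjects ≤ dropout × arm size = 0.20 × 205 = 41.

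For an assumed dropout of 10% to 30%: 0.10 × 205 = 20.5 and 0.30 × 205 = 61.5, or about 21 to 62.

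This is an upper bound. It requires every SMT dropout to be reachable for a visit and every site to follow 5.3.5 rather than the schedule. Albutein subjects who were never infused would add to it. The documents give no number for them; the first infusion is due on the day of randomization, so few are expected.

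**The case against.** The strongest reply is that 5.3.5 says what IP recipients should have and exempts nobody. Protocol 7.2.1 sends readers to Appendix 1 for visit procedures, and that schedule includes the visit without an IP condition. On this view a site would carry it out in both arms, and the sentence is merely loose. That stands in part: a reader might infer that SMT dropouts do miss the visit, and the documents do not establish it. What remains is that the section specific to withdrawal is narrower than the rest. A site that omitted the visit could cite it, and the omission might not be logged as a deviation.

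A second inference is that refractory ascites, the seventh gated secondary endpoint, would be biased. The mechanism is weak. The criteria in Protocol Appendix 2 rest on a week of intensive diuretics with non-response over days, recurrence within weeks, or diuretic complications, so one extra visit does not readily produce a new case. Ascites is already assessed monthly in both arms, SAP 9.2.7 counts by start date, and the mapping in SAP 6.1.5 is for exploratory endpoints.

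A third inference puts a number and a direction on the effect. Applying a 10–20% yield of new events to 41 leavers gives about 4 to 8 extra Albutein events, or 2–4% of 205. The yield appears nowhere in the documents, and the figure pools refractory ascites with ACLF, which are separate endpoints. Nor is a bias against Albutein shown. Subjects may withdraw simply at their own request (Protocol 5.3.3), so values at dropout need not be poor. Those who stop treatment for transplant, a listed severe adverse event or, at the investigator's discretion, TIPS continue planned visits (Protocol 5.3.2), so many deteriorating subjects fall outside 5.3.5.

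**Conclusion.** The contradiction is real and rests on wording alone. Protocol 5.3.5 conditions the ED visit on receipt of Albutein; Protocol 7.2.1.2.4, Appendix 1 and SAP 5.2.5 do not. The consequence is a risk rather than an established loss: assessment at dropout could differ by arm if sites follow 5.3.5 literally.

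The risk falls on ACLF incidence, on the scores that need bedside findings (CLIF-C OF, CLIF-C ACLF, Child-Pugh), less on MELD and CLIF-C AD, and on the end of adverse event recording. Any effect on refractory ascites is likely small, and the primary and time-to-event secondary endpoints are largely unaffected. At most about 41 of 205 SMT subjects are exposed under the plan's 20% dropout assumption. The point is worth correcting because the rule as written is wrong and the correction is cheap; it does not threaten the main inference.

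**What to change.** In 5.3.5, replace the condition on IP so that the sentence covers all randomized subjects in either treatment group who discontinue early from the study, whether or not they received IP. Leave the visit procedures and timing as they stand. This brings the section into line with 7.2.1.2.4, Appendix 1 and SAP 5.2.5.

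The cost is one sentence in a protocol amendment. It adds no procedure that the schedule lacks.

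SAP section 12 refers to enrolment in the past tense, so it may be too late for an amendment to change what sites do. If follow-up has ended:
- Report, by arm, how many early leavers had the ED visit and how many did not.
- Repeat the affected exploratory analyses (ACLF incidence and the repeated-measures score models) without ED-visit data, and state whether the conclusions change.

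Both use data already collected and need only a short addition to the SAP or the study report.

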6 TREATMENT OF SUBJECTS

See Section 4.4 for the treatment(s) to be administered, including the name(s) of all the product(s), the dose(s), the dosing schedule(s), the route/mode(s) of administration.

6.1 Administration and Timing of Investigational Products for Each Subject

6.1.1 Albutein 20% Dosage, Procedures, and Treatment Regimen

Randomization must occur within 72 hours of screening, and it can occur while the subject is hospitalized or after discharge from the hospital. The first dose of Albutein 20% is administered on the same day as randomization at a dose of 1.5 g/kg body weight (maximum 100 grams per subject). Thereafter, subjects will receive Albutein 20% infusions at the dose of 1.5 g/kg body weight (maximum 100 grams per subject) every 10 ± 2 days for the rest of the study (up to a maximum of 12 months). At each administration, the infusion rate should be 4 mL/min.

6.1.2 Standard Medical Treatment

Standard medical treatment will be administered within 3 days (72 hours) of screening, and following randomization, per institution standards. Several guidelines are published for the management of decompensated cirrhosis (2-5). Subjects will receive SMT (see Section 4.4.1.2) for the length of the study or as long as needed.

6.2 **Prior and Concomitant Therapy**

Prior (within 30 days prior to screening) and concomitant medications must be recorded in the eCRF and subject's source documents, including the trade or generic names of the medication, the dose, the route of administration, and the duration of the medication (frequency).

Any medication administered during the study (including any blood products) will be recorded on the eCRF and subject's source documents with the exception of anesthesia related products, fluid replacement therapies, and electrolyte supplementation. In addition, products administered at different doses on the same day to manage and maintain vital functions (eg, insulin, furosemide) will only be recorded once on the eCRF and subject's source documents with the dosage reported as pro re nata.

In the event that an AE or suspected adverse drug reaction (ADR) should occur, complete details of all concomitant medications administered will be reported to the sponsor.

Usual treatments in decompensated cirrhosis will be allowed.

Treatment with terlipressin and albumin will be allowed in both treatment groups only in subjects developing type-1 HRS according to the ICA criteria (Appendix 2).

6.2.1 Prohibited Medications Prior to Study Participation

Subjects receiving dual anti-platelet therapy or anti-coagulant therapy prior to enrollment (within 7 days prior to enrollment [exception: DVT prophylaxis]) cannot be included. In addition, subjects with HCV receiving antiviral therapy within 14 days prior to enrollment cannot be included.

6.2.2 Prohibited Concomitant Medications during the Study

Use of the following medications is prohibited during the study participation:

Albumin dialysis will not be allowed during the treatment period in the SMT + Albutein 20% treatment group.

6.2.3 Restricted Concomitant Medications during the Study

This section describes medications that are restricted but not prohibited during the study participation:

Platelet transfusion will be made in cases of severe thrombocytopenia (<20,000/mm³), or in the case of bleeding complications when the platelet count is below 50,000/mm³.

6.2.4 Cardiac Overload/Pulmonary Edema Treatment

In subjects with the diagnosis of cardiac overload/pulmonary edema, standard protocols will be applied as per institution standards and may include fluid restriction, IV administration of furosemide, and Renal Replacement Therapy if clinically indicated (diuresis lower than 0.5 mL/kg under high doses of furosemide). See Appendix 9 for an example of Algorithm for Cardiogenic Pulmonary Overload and Appendix 10 for guidelines on the management of pulmonary edema.

6.3 Treatment Compliance

Reasons for any deviation from the administration of less than 100% of the IP dose as prepared by the pharmacist or designee must be recorded in the eCRF and in the subject's medical records.

7 ASSESSMENT OF EFFICACY

7.1 Efficacy Variables

7.1.1 Primary Efficacy Variable

• Time to liver transplantation or death through 1 year after randomization.

7.1.2 Secondary Efficacy Variables

- Time to liver transplantation or death through 3 and 6 months after randomization, and time to death through 3 and 6 months after randomization
- Time to death through 1 year after randomization
- Total number of paracenteses and incidence of refractory ascites according the ICA criteria (Appendix 2)

7.1.3 Exploratory Variables

- Incidence of ACLF (3, 6, and 12 months)
- Organ function subscores (liver, renal, cerebral, coagulation, circulation, and respiration), according to the CLIF-C OF score and the total CLIF-C OF score (Appendix 3)
- Number and length of hospital readmission for an acute complication of cirrhosis
- Number and length of ICU admission
- Incidence of disease-related complications (see Section 8.3.10)
- Serum albumin concentration and albumin functional capacity in serum (albumin binding capacity [Table 7-1])
- Incidence of insertion of TIPS for refractory ascites
- CLIF-C ACLF score ,CLIF-C AD score, MELD score, and Child Pugh score
- Quality of life: EQ-5D-5L health questionnaire (Appendix 5)

7.2 Methods and Timing for Assessing, Recording, and Analyzing Efficacy Parameters

7.2.1 Observations and Measurements

The following is a description of the procedures/assessments to take place at each study visit. See the Schedules of Study Procedures and Events in Appendix 1.

7.2.1.1 Screening Visit

Following signature of the informed consent form (ICF), subjects will be screened while hospitalized. Local laboratory testing will be used for screening to determine inclusion and exclusion criteria have been met, prior to initiating treatment. Local laboratory tests performed for screening purpose only will be kept in subjects' source documents but will not be entered into the eCRF. In addition, Central Laboratory testing will be collected for the purpose of safety assessment and data analyses.

If a subject is ineligible for participation, their demographic data and specific reason for ineligibility will be captured on the subject's source documents and eCRF.

The screening assessments and activities will include:

- Assign subject number
- Add subject's data into the Screening Log
- Review of the inclusion and exclusion criteria which include local labs (see Sections 5.1 and 5.2, respectively) to determine subject's eligibility
- Documentation of demographics: date of birth, gender, race, and ethnic origin
- Documentation of medical history, including etiology of cirrhosis, history, and significant concomitant disease conditions
- Urine pregnancy test (human chorionic gonadotrophin [HCG]-based urine assay) for women of childbearing potential (to be performed locally at the investigative study center)
 - Women of child-bearing potential include any female who has experienced menarche and who has not undergone successful surgical sterilization (hysterectomy, bilateral tubal ligation or bilateral oophorectomy) or is not postmenopausal (postmenopausal is defined as amenorrhea for more than 12 consecutive months or women on hormone replacement therapy with documented serum follicle stimulating hormone level <35 mIU/mL). Women who are using oral, implanted, or injectable contraceptive hormones or mechanical products such as an IUD or barrier methods to prevent pregnancy or practicing abstinence or where their sexual partner is sterile (eg, vasectomy) should be considered to be of child-bearing potential.
- Full physical examination (excluding breast and genitourinary examination)
- Ascites assessment according to the ICA criteria (Appendix 2)
- Hepatic encephalopathy evaluation (Appendix 4)
- Hemodynamics assessment (mean arterial pressure [MAP])

- Peripheral capillary oxygen saturation (SpO₂) assessment
- Blood sample collection for:
 - Clinical laboratory assessments (eg, hematology, chemistry, coagulation)
- Illness severity scores evaluation: CLIF-C OF score, CLIF-C AD score, CLIF-C ACLF score, MELD score, and Child Pugh score (Appendix 3).
- Record endoscopic findings (if performed in the last 6 months)
- Record abdominal ultrasound (if performed in the last 6 months)
- Record ACLF grade (see Table 2-1)
- Record prior (within the last 30 days) concomitant medications
- Record AEs

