5.2 Exclusion Criteria

A subject meeting any of the following exclusion criteria is NOT eligible for participation in the study.

1v5. Subjects with ACLF at Screening.

87 Ъ 24-Sep-2020 30 Effective Date Page Effective
 Number
 GLB-PRT-ALB-IG1601
 Version
 6.0
 Status
 Errect

 IG1601 - Prevention of Mortality with Long-Term Administration of Human Albumin in Subjects with
 6.0
 Status
 errect
Version 6.0 Decompensated Cirrhosis and Ascites GRIFOLS **Bioscience Industrial Group**

- 2v5. Subjects with type 1 HRS currently on treatment with vasoconstrictors or hemodialysis.
- 3. Subjects with TIPS or other surgical porto-caval shunts.
- 4v5. Subject with refractory ascites as defined by ICA criteria without any other event of acute decompensation (Appendix 2).
- 5v5. This criterion has been removed from protocol Version 5.
- 6v5. Subjects receiving dual anti-platelet therapy or anti-coagulant therapy (exception: DVT prophylaxis).
- 7v5. Subjects with ongoing endoscopic eradication of esophageal varices with ≤ 2 endoscopic sessions completed before screening.
- 8v5. This criterion has been removed from protocol Version 5.
- Subjects with evidence of current locally advanced or metastatic malignancy. Subjects with hepatocellular carcinoma within the Milan criteria [1 nodule ≤5 cm or 3 nodules ≤3 cm] [Appendix 6], non-melanocytic skin cancer, or controlled breast or prostate cancer can be included.
- 10v4. Subjects with acute or chronic heart failure (New York Heart Association [NYHA] Appendix 7).
- 11. Subjects with severe (grade III or IV) pulmonary disease (Global Obstructive Lung Disease [GOLD] Appendix 8).
- 12v5. Subjects with nephropathy with renal failure with a serum creatinine $\geq 2 \text{ mg/dL}$ or systemic hypertension.
- 13v5. This criterion has been removed from protocol Version 5.
- 14. Subjects with severe psychiatric disorders.
- 15. Subjects with a known infection with human immunodeficiency virus (HIV) or have clinical signs and symptoms consistent with current HIV infection.
- 16. Females who are pregnant, breastfeeding, or, if of childbearing potential, unwilling to practice effective methods of contraception (oral, injectable, or implanted hormonal methods of contraception, placement of an intrauterine device (IUD) or intrauterine system, condom, or occlusive cap with spermicidal foam/gel/cream/suppository, male sterilization, or true abstinence*) throughout the study.

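### The FSH criterion for postmenopausal status appears to run in the wrong direction, and the sentence joining it to sterilization is also faulty; few women, possibly none, are affected

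*Protocol*

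**What the plan says.** Protocol Section 7.2.1.1 holds the only definition of child-bearing potential in the documents. It includes any female past menarche "who has not undergone successful surgical sterilization (hysterectomy, bilateral tubal ligation or bilateral oophorectomy) or is not postmenopausal". It then states that "postmenopausal is defined as amenorrhea for more than 12 consecutive months or women on hormone replacement therapy", and the second of these routes is completed as "women on hormone replacement therapy with documented serum follicle stimulating hormone level <35 mIU/mL". The two routes are alternatives, so the hormone-therapy route requires no period of amenorrhea.

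The following sentence places other women inside the child-bearing group whatever precautions they take. It begins "Women who are using oral, implanted, or injectable contraceptive hormones" and goes on to devices, barrier methods, abstinence and a sterile partner. It does not mention hormone replacement therapy.

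Two rules depend on the definition:

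- The screening procedures require a "Urine pregnancy test (human chorionic gonadotrophin [HCG]-based urine assay) for women of childbearing potential".
- Exclusion criterion 16 (Protocol Section 5.2) excludes "Females who are pregnant, breastfeeding, or, if of childbearing potential, unwilling to practice effective methods of contraception".

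Protocol Table 7-1 and the schedules of events (Appendix 1 of the protocol and of the SAP) place the pregnancy test at screening only. FSH is not among the tests in Table 7-1. Nothing elsewhere in either document gives a different FSH limit or direction.

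**The concern.** FSH rises when ovarian function ceases. A ceiling on FSH therefore admits women whose ovaries still work and women whose FSH is held down by the hormones they take. It leaves out women whose raised FSH would support menopause. A low value in a woman on hormone therapy cannot tell these groups apart, so it cannot serve as evidence of menopause.

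What is at stake is participant safety and the correct application of criterion 16. A woman taken out of the child-bearing group by this clause would have no required pregnancy test at screening and no contraception requirement during up to 12 months of treatment. No later scheduled test would reveal the misclassification.

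**Working it through.** No sample-size, power or event figure bears on this point, so the check is one of logic.

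**Inputs.** From Protocol Section 7.2.1.1, write S for surgically sterilized, A for amenorrhea of more than 12 months, H for on hormone replacement therapy, and L for a documented FSH below 35 mIU/mL. The definition of postmenopausal is then

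P = A or (H and L).

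**Joining words.** Among women past menarche:

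- Literal reading: of child-bearing potential = (not S) or (not P). A woman leaves the group only if she is both sterilized and postmenopausal. For any unsterilized woman P then changes nothing, so the postmenopausal clause is idle for her. Sterilization alone would not be enough to leave the group either.
- Evident intent: of child-bearing potential = (not S) and (not P). Either condition takes her out.

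**Result for an unsterilized woman on hormone replacement therapy:**

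| Amenorrhea > 12 months | Documented FSH | Postmenopausal | Child-bearing group, literal | Child-bearing group, intent |
|---|---|---|---|---|
| Yes | Any or none | Yes | In | Out |
| No | Below 35 | Yes | In | **Out** |
| No | 35 or above | No | In | In |
| No | None | No | In | In |

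The FSH clause decides the outcome only in the second and third rows, and only on the intended reading. There the low value removes the woman from the group and the high value keeps her in, which is the opposite of what the physiology would lead one to expect.

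**Consequence.** The woman in the second row is outside the pregnancy test, because Section 7.2.1.1 limits it to women of childbearing potential. She is also outside the contraception part of criterion 16, which carries the same condition. Table 7-1 and Appendix 1 list the test without repeating that limit, so a site might test more widely, but the procedure text does not require it.

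**Size.** The documents do not give the number of women on hormone therapy. Purely as an illustration, assume that 30% to 40% of the 410 planned subjects are women, and that 1% to 3% of those are on hormone therapy without 12 months of documented amenorrhea:

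- Low: 410 × 0.30 × 0.01 = 1.2
- High: 410 × 0.40 × 0.03 = 4.9

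That gives about 1 to 5 women before the remaining condition is applied. The clause also needs a documented FSH, which the protocol does not collect. Under these assumptions the range is therefore a ceiling, and zero is plausible.

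**The case against.** The strongest reply is that the definition, followed to the letter, does no harm: every unsterilized woman stays in the child-bearing group and is tested. That is correct as a literal reading. A reader might infer that sites following the text exactly will skip the test, and the text does not support that. The omission arises only on the intended reading. The literal reading, however, leaves a carefully drafted postmenopausal clause without effect for the women it is meant to sort, so it can hardly be what was meant. The reply exposes a second defect in the sentence and does not clear the first.

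A second reply is that neither document gives an FSH reference range, so the direction rests on general physiology. That stands as a limit, and it is why the request is to verify the sign and not to substitute another.

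Other stronger readings are tempting but not supported:

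- *The section contradicts itself.* The sentence on contraceptive hormones covers different women and says nothing about FSH. It takes a more cautious approach to hormone users, but it is not a strict contradiction.
- *Every woman reached by the clause is misclassified.* Some women with low FSH on hormones are truly postmenopausal. The defect is that the criterion cannot distinguish them.
- *Postmenopausal women with high FSH are wrongly held to contraception.* More than 12 months of amenorrhea qualifies a woman whatever her FSH, so this could arise only without that history.

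Several mitigating facts also stand. Known pregnancy excludes a woman regardless of classification. Pregnancies from first exposure to 28 days after the last dose must be reported (Protocol Section 8.3.11.3). Screening-only testing applies to all women and does not come from this clause. The product risks in Protocol Section 2.3 name no reproductive hazard. SAP Section 12 says that most patients were enrolled under the final amendment, so a change to the screening definition may now reach few new subjects.

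**Conclusion.** The point holds as a minor correction bearing on participant safety. The FSH limit appears reversed, and the words joining sterilization and menopause do not say what they must mean. If they are read as intended, a woman on hormone therapy with a low documented FSH and no 12-month amenorrhea escapes both the pregnancy test and the contraception requirement, with no later scheduled test.

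The number affected is probably very small and may be none. No endpoint, analysis population, power figure or part of the primary analysis is touched. The conclusion rests on two premises outside the literal text: that FSH rises at menopause, and that the definition means neither sterilized nor postmenopausal.

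**What to change.** By a clarification letter or amendment, the sponsor should:

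1. Verify the direction and value of the FSH clause in Protocol Section 7.2.1.1, and reconcile it with the rest of that definition and with exclusion criterion 16.
2. Reword the link between sterilization and postmenopausal status so that the sentence has one clear meaning.
3. Check whether any enrolled woman was classified as postmenopausal by the FSH clause alone, and record the result.

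No replacement threshold and no interim clinical rule is proposed; those are for the sponsor to settle. The cost is one corrected sentence and a short check of screening records for women on hormone therapy.
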